#### 5.3 Unscheduled Visits

The study coordinator and investigators will be available to address any concerns or questions that may arise during the study. Any medically related questions will be referred to their primary treating physician.

#### 5.4 **Prior and Concomitant Medications**

All medications used within 7 days prior to the screening visit and through the end of the study will be recorded. The dates of administration and reason for use will be included. Participation in the study will not preclude subjects from receiving symptomatic management for concussion related symptoms (e.g. non-steroidal anti-inflammatory drugs for headaches) or other disorders. However subjects will be discontinued from the study if they use neurological or psychoactive medications (e.g. stimulants, antidepressants, anticonvulsants, benzodiazepines, etc.) during the study. While subjects will be prohibited from using dietary supplements during the study, there will be no dietary restrictions.

#### 5.5 Rescue Medication Administration

Subjects who experience side effects from the study medication, to a level that the subject requests medication to manage these symptoms, will be discontinued from the study.

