# 4.3.2 Total Number of Study Sites/Total Number of Subjects Projected

The study will be conducted through the Children's Hospital of Philadelphia and the Hospital of the University of Pennsylvania. Recruitment will stop when 50 subjects who are evaluable for efficacy are enrolled. A subject who is evaluable for efficacy is one who completes the study up until at least day 10 of the study. It is expected that approximately 72 subjects will be enrolled to produce 50 such subjects. All subjects who enroll and receive study medication will be evaluable for safety.

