#### 5.6 Subject Completion/Withdrawal

Subjects may withdraw from the study at any time without prejudice to their care. They may be discontinued from the study at the discretion of the investigators for safety concerns related to any adverse event. Any subject who sustains a second concussion during the study period will be withdrawn. Additionally, any female subject who becomes pregnant while enrolled in the study will be withdrawn. Date of termination will be documented for each subject.

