# 5.7 Early Termination Study Visit

The study coordinator will contact subjects who terminate early and request that they return all of the study drug bottles (used and unused).

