## 7.3.2 Primary Efficacy Analysis

The primary intent to treat analysis will include all subjects who enroll and contribute at least 10 days of data to the study. The mean trajectory in decline and recovery in processing speed is unknown. Thus the primary analysis will aim to determine whether there are differences in processing speed between the BCAA dose groups and placebo, and if so, at what time periods the differences are most pronounced. The primary analysis will focus on results for the first 10 days of the study when we anticipate that the majority of subjects will be highly compliant. We will model processing speed as a function of dose and day of study and will allow differences between dose groups to vary as a function of time through a series of interaction terms. To ensure that the number of interaction terms does not become too large, we will consider groups of two to four time points, looking specifically at whether

04/06/2018 V 0.16

there are differences between any of the dose groups and placebo at Days 1-2, 3-6, 7-10, 11-14, 15-18, 19-21. The primary analysis will consider three key time periods, Days 3-6, 7-10 and 11-14 when we expect differences in processing speed between the BCAA-treated groups and placebo to be largest. Since processing speed differs with age, the model will be adjusted for age to account for any imbalances in age between dose groups. A mixed effects model will be used to account for correlations between repeated measurements on individual subjects. Likelihood ratio tests will be employed to specifically test whether there are differences in mean processing speed between placebo and any of the BCAA doses at the three key time periods. These three global tests will be conducted at a family-wise error rate of 0.05, using a Bonferroni correction to account for the three individual global tests. If statistical significance is achieved for the global test, we will then compare individual dose levels to placebo within time periods, again using a correction for four multiple tests per key time period.

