#### 10.4.2 Risk Assessment

Risks for this study are a minor increase above minimal. Subject safety will be monitored by AE's on a weekly basis. Expected adverse experiences during this study may include gastrointestinal symptoms such as dyspepsia either from the BCAA's themselves or the 20 ounces of fluid consumed. Prior studies have shown that these symptoms when related to BCAA's are mild and transient. An informal inquiry of athletes (both male and female) from many sports indicated that drinking 20 ounces of fluid twice daily is not burdensome and within the volume typically consumed while training or competing. Should a subject report new onset gastrointestinal symptoms while on therapy, the subject will be monitored to see if these symptoms either have an alternative explanation (e.g. development of acute gastroenteritis from an identifiable source) or spontaneously resolve in less than 24 hours. The study therapy will not be held unless these symptoms persist for more than 24 hours or are severe enough to require medical attention. In this case the subject will be removed from the study and the therapy not restarted. Taking the CCAT or CDP may temporarily exacerbate concussion symptoms, which typically resolve after a short period of rest. Neurological and psychiatric symptoms induced by changes in neurotransmitters like serotonin, dopamine, norepinephrine are theoretically possible with BCAA therapy but have never been observed clinically. Emergence of any of these symptoms will result in discontinuation of the subject's participation in the study. BCAA therapy will be discontinued for any SAE related to its use.

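### Side-effect stops end study participation, not only the drink, so an early stop removes a randomized subject from the primary intent-to-treat analysis

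*Combined protocol and SAP*

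**What the plan says.** Three rules end participation because of side effects.

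- Section 5.5: a subject with side effects from the study medication "to a level that the subject requests medication to manage these symptoms, will be discontinued from the study".
- Section 10.4.2, gastrointestinal symptoms lasting beyond 24 hours or needing medical attention: "In this case the subject will be removed from the study and the therapy not restarted".
- Section 10.4.2, neurological or psychiatric symptoms: "Emergence of any of these symptoms will result in discontinuation of the subject's participation in the study".

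Section 5.6 is permissive: subjects may be "discontinued from the study at the discretion of the investigators for safety concerns related to any adverse event". For related serious adverse events, 10.4.2 says "BCAA therapy will be discontinued for any SAE related to its use" and is silent on whether the subject stays in the study.

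After early termination, 5.7 describes one action: "The study coordinator will contact subjects who terminate early and request that they return all of the study drug bottles". No further cognitive testing is mentioned.

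Section 7.3.2 sets the analysis population: "The primary intent to treat analysis will include all subjects who enroll and contribute at least 10 days of data to the study". Evaluability is worded differently. Section 4.3.2 states "A subject who is evaluable for efficacy is one who completes the study up until at least day 10 of the study", and 7.4 likewise asks for data through Day 10.

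**The concern.** An intent-to-treat comparison keeps randomized subjects in their assigned arm whatever happens afterwards. Here a reaction to the assigned drink can decide who is analyzed. Those left out may differ on the outcome: section 2.4 raises impaired cognition as a theoretical effect of BCAA's, while noting that it has not been seen clinically.

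Two kinds of information are lost. Results already collected are set aside by the 10-day minimum. Later results are never collected, and no change to the analysis set can bring those back. Section 4.3.2 also recruits until 50 evaluable subjects are reached, so subjects lost this way are in effect replaced by others who reach Day 10. One purpose of the trial (section 3) is to find the most promising dose, so exclusion driven by tolerability touches what the trial is meant to learn.

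**Working it through.** **Which stops exclude a subject.** Daily testing runs from Day 0 to Day 21, and the key periods are Days 3-6, 7-10 and 11-14.

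| Drink stopped | Days of data possible | 7.3.2 (10 days of data) | 4.3.2 and 7.4 (through Day 10) | Effect on the key periods |
|---|---|---|---|---|
| Day 7 | at most 8 (Days 0-7) | excluded | excluded | all four Days 3-6 results may exist but go unused |
| After the Day 9 test | up to 10 (Days 0-9) | may be included | not evaluable | the two definitions disagree |
| After the Day 10 test | up to 11 (Days 0-10) | may be included | evaluable | no data for Days 11-14 |

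Section 7.3.2 plans to explore missing-data patterns, but that does not return anyone with fewer than 10 days of data to the primary set.

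**The plan's own figure.** Inputs from 7.4: 10 subjects per arm, three measurements per period, SD 0.10 s, intra-class correlation 0.5, two-sided alpha 0.05/4 = 0.0125, power 80%.

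- SD of a three-day mean = 0.10 × √((1 + 2 × 0.5)/3) = 0.0816 s
- Detectable difference = √(2/10) × 0.0816 × (2.498 + 0.842) = 0.122 s

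This reproduces the stated 0.122 s.

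**How many subjects.** No stop rate is given. The only related figure is in 2.4: gastrointestinal symptoms in 12% of a BCAA group with liver cirrhosis. That is a symptom rate, not a stop rate, in a population that the protocol itself calls different. Enrolment per arm is 72/5 = 14.4, and 0.12 × 14.4 = 1.7. I therefore assume 0 to 2 exclusions per arm.

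**Shift in the arm mean.** If k subjects are left out, 10 are kept, and the two groups differ by d SD (an assumption), the shift is k/(10 + k) × d × 0.0816 s.

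| k | d = 0.5 | d = 1 |
|---|---|---|
| 0 | 0 | 0 |
| 1 | 0.0037 s (3.0% of 0.122) | 0.0074 s (6.1%) |
| 2 | 0.0068 s (5.6%) | 0.0136 s (11.2%) |

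The periods in 7.3.2 span four days. With four-day means the SD is 0.10 × √((1 + 3 × 0.5)/4) = 0.0791 s, and the d = 1 shifts become 5.9% and 10.8%.

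**Dilution if stoppers are kept.** Suppose 2 of 12 subjects in an arm are off the drink for a whole period and lose the effect at once. A 0.122 s difference becomes 0.122 × (1 − 2/12) = 0.102 s. With 12 subjects in each of the two arms compared, 0.102/(0.0816 × √(2/12)) = 3.05, and 3.05 − 2.498 = 0.55, so power is about 71%.

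**The case against.** The strongest objection is that the stop rules are not the main cause. The 10-day minimum in 7.3.2 drops anyone with too little data, for any reason. A mixed model without it would use the Days 3-6 results of a Day 7 stopper with no change to any stop rule. This stands, so the remedy must lift the minimum for these subjects as well as change the stop rules. It is not a complete answer, because results from Day 8 on would still not exist.

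Safety is the second objection. Section 10.4.2 warns that the cognitive test may briefly worsen symptoms, and ending participation when neurological or psychiatric symptoms emerge in subjects as young as 11 is defensible. The drink can be stopped just as fast while testing stays optional and subject to the investigator's judgement. Some subjects will still be lost. Section 5.4 would also still remove anyone who takes psychoactive medication.

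Third, the trial is exploratory, plans for 72 enrolled to give 50 evaluable, and will study missingness. That lowers the stakes. It does not make the intent-to-treat label fit the set described.

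A reader might go further and infer that the BCAA comparisons are biased in a known direction, or that the type I error is materially inflated. The documents do not support this. Section 10.4.2 describes BCAA-related gastrointestinal symptoms as mild and transient, and also attributes such symptoms to the 20 ounces of fluid that every arm drinks, so losses may occur in any arm and partly offset. As a harsher illustration, let one arm alone lose 12%, with stopping correlated 0.25 to 1 with slow processing. The spurious difference is then 0.005 to 0.019 s, and the per-contrast error rises from 0.0125 to 0.013-0.025. Nothing in the documents establishes that pattern. The planned loss of 22 of 72 (30.6%) covers all causes and should not be read as a tolerability rate.

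**Conclusion.** The point holds as a matter of structure. Sections 5.5 and 10.4.2 end participation, 5.7 collects only bottles, and 7.3.2 then leaves early stoppers out of the primary analysis.

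Its size is probably small: 0 to 0.014 s per arm mean, or 0% to 11% of 0.122 s. That range rests on three assumptions: 0 to 2 exclusions per arm, an outcome difference of 0.5 to 1 SD, and no offsetting loss in the comparator arm. The direction is unknown.

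Two wider readings should be avoided. Not every safety stop is written as removal: 5.6 only permits it, and the related-SAE sentence names therapy alone. The safety analysis is also unaffected, since 7.3.4 covers every enrolled subject who receives study medication. The change is worth making because it is cheap and because tests not taken cannot be recovered later.

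**What to change.** 1. In 5.5, 10.4.2 and the adverse-event sentence of 5.6, replace removal from the study with: *The study drink will be stopped and not restarted. The subject will be asked to continue the daily web assessments to Day 21, unless the subject withdraws or the investigator judges the assessments unsafe.* Add the same request to 5.7.
2. In 7.3.2, include subjects who stop the drink for side effects in their assigned arm, with all available data in the mixed model and without applying the 10-day minimum to them. Add a sensitivity analysis that leaves out data after the drink was stopped, also without the minimum. With the minimum in force, early stoppers would drop out again and the analysis would largely repeat the present plan.
3. Sections 2.2 and 5.2 show that the trial is already enrolling. Apply the new stop rule going forward, and report how many subjects were removed under the present one, because the two groups will have different follow-up.

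The cost is a few sentences of protocol text and a short change to the analysis section. The web assessments, the per-day payment (10.7) and a zero-bottle answer (Appendix 4) already exist. The main downside is dilution by off-drink days, to about 0.102 s in the case worked above; the sensitivity analysis shows the other view. Some subjects will decline to continue, and their later results will still be missing.

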#### 5.6 Subject Completion/Withdrawal

Subjects may withdraw from the study at any time without prejudice to their care. They may be discontinued from the study at the discretion of the investigators for safety concerns related to any adverse event. Any subject who sustains a second concussion during the study period will be withdrawn. Additionally, any female subject who becomes pregnant while enrolled in the study will be withdrawn. Date of termination will be documented for each subject.

# 5.7 Early Termination Study Visit

The study coordinator will contact subjects who terminate early and request that they return all of the study drug bottles (used and unused).

### **6** STUDY EVALUATIONS AND MEASUREMENTS

#### 6.1 Screening and Monitoring Evaluations and Measurements

#### 6.1.1 Demographics

• Demographic characteristics will be obtained via interview: date of birth, gender, ethnicity, racial background, native language, handedness, and highest educational level attained.

#### 6.1.2 Concussion History

- Concussion history will be obtained via interview: number of times diagnosed with a concussion and date of last concussion.
- History of current concussion obtained from the subject and family members, if necessary, via interview including: mechanism of injury, for sports-related concussions: sport and position and specific mechanism (head-to-head, head-to-ground, hit-to-body, etc), day and time of the injury, was the subject helmeted, presence and duration of loss of consciousness. The subject may bring a clinic note from their referring physician and refer to it for answers to these questions if they are unsure or sustained amnesia from their concussion. For CHOP patients, data may be collected directly from the medical record of their CHOP visits if subjects/parents are unable to provide.

### 6.1.3 Height and weight

Height and weight will be measured, or taken from the most recent visit documentation if visit was within 1 week of enrollment.

#### 6.1.4 Laboratory Evaluations

#### 6.1.4.1 Pregnancy Testing

A urine pregnancy test will be performed through the Translational Core Laboratories for all post-menarchal female subjects. Results will be available to the study coordinator and investigators in less than 5 minutes. If the study team is unable to access Translational Core Laboratories and/or it is not possible to obtain pregnancy test results within 5 minutes, the pregnancy test will be done by the enrolling study team member. The enrolling study team member must have documented training to do the pregnancy test. If a pregnancy test was performed by a medical facility within 72 hours prior to enrollment, and documentation can be provided or found in the CHOP medical record, then a second pregnancy test will not be required. Pregnant subjects will be excluded from the trial. Should a subject become pregnant while enrolled in the study, they will be withdrawn.

#### 6.2 Efficacy Evaluations

## 6.2.1 Axon Sports Computerized Cognitive Assessment Tool (CCAT)

The Axon Sports CCAT will be completed daily over an 8-10 minute period using any computer with internet access. The CCAT consists of four computerized cognitive tests,

derived from theoretical and developmentally sensitive principles and aims to be sensitive to any cause of cognitive performance change in individuals over time. The tasks themselves measure processing speed (via a simple reaction time task), attention (via a choice reaction time task), learning (via a one card learning task), and working memory (via a one-back task). All of the four tasks are based on a 'playing-card' paradigm. Within each of the playing-card tasks, participants are shown a picture of a playing card and asked to answer a question about the card. Different tests are created by changing the question. For example, in the attention test the question 'Is the card red?' elicits a simple binary choice and is equivalent to a choice reaction time test. The question 'Is the card exactly the same as the previous card?' is used in the working memory paradigm to produce a 1-back version of the commonly used n-back working memory paradigm. In all tasks, responses are indicated by pressing the 'YES' or 'NO' buttons on a computer keyboard. Subjects will be reminded to choose an environment with minimal distractions for completing the cognitive battery. Subjects will complete a single short practice session, as previous research has demonstrated that a single practice test is sufficient to eliminate the majority of practice effects.

#### 6.2.2 Clinical Symptoms Checklists

A 9 item clinical symptom checklist, designed to measure the overall duration and severity of concussion-related symptoms, will be administered daily over a 1-2 minute period via the study website. This summative 7-point Likert-type scale instrument incorporates aspects of the two scales commonly used in the literature (Post-concussion Symptom Scale [included in the Sport Concussion Assessment Tool 2 (SCAT2)] and Graded Symptom Checklist) to capture the overall severity of symptoms. The checklist will be administered twice: first to address the duration and second the severity of symptoms including headache, nausea, balance problems, sleeping more than usual, drowsiness, fatigue, feeling "slowed down" or "in a fog", and difficulty concentrating.

#### 6.2.3 Cognitive and Physical Activity Assessments

Subjects will be asked daily to indicate their level of cognitive and physical activity via the study website. The physical activities are based on the "Graduated Return to Play" protocol recommended in the Consensus Statement on Concussion in Sport. The cognitive activities are based on return to school guidelines used at CHOP.

#### 6.2.4 Actigraphy Sleep and Assessment

Subjects will complete a daily brief questionnaire on their sleep via the study website and will be asked to wear an actigraphy monitor throughout the trial on the non-dominant wrist, with the exception of bathing or swimming. Actigraphy has been shown to provide a valid estimate of sleep patterns in children and adolescents. An actigraph is a non-invasive small, wristwatch sized activity monitor that provides an estimate of sleep patterns based on data collected by an internal accelerometer, and can record and store the data over an extended period of time. The data are collected continuously and then translated into epochs (typically 30 sec or 1 min) of activity. Using validated algorithms, epochs are then scored as sleep or wake. Subjects will be instructed to push the event button on the device each time they go to bed, get out of bed, take the watch off or put the watch back on if not permitted in

an academic or athletic event. The study coordinator will download the data from the actigraph device onto a study computer at each study visit and the conclusion of the study.

The actigraph monitor used in this study is called the ActiSleep+ Monitor and is produced by the ActiGraph Company from Pensacola, FL. This product is approved for marketing in the US and is an FDA cleared Class II medical device within the US (see attached material). This product is currently deployed in other concussion research studies at CHOP.

### 6.2.5 Computerized Dynamic Posturography (CDP)

Computerized dynamic posturography (CDP) will be measured over a 15 minute period at visits 1, 2, and 3 at The Balance Center at the Hospital of the University of Pennsylvania. CDP is a postural control test utilized to assess function balance ability. The Sensory Organization Test of CDP evaluates a person's ability to effectively utilize the visual, somatosensory, and vestibular systems for the maintenance of balance. It also provides information regarding the patient's ability to maintain balance in the presence of inaccurate visual information that can confuse orientation. The motor control test measures, time to respond to a disruption of equilibrium. Testing is performed by standing a subject on a computerized support surface to measure their ability to sustain upright stance while the support surface and/or visual surround move in response to their own postural movements. Six sensory conditions are performed to assess ability to use visual, proprioceptive, and vestibular information in isolation and in concert for the preservation of balance. Medium and large forward translations for each leg will be recorded for the motor control test.

CDP will be performed on an EquiTest® system (manufactured by NeuroCom®, a division of Natus®) which is an FDA approved product. CDP will be conducted by a trained audiologist A report will be issued to the investigators who will subsequently input the results into the study database.

Balance testing is now available at CHOP, as of fall 2017, and if equivalence can be determined between the results gathered at HUP and CHOP and access can be gained to this equipment/lab then CHOP will also be added as a potential site for balance testing of subjects.

